8.2.2 Analysis of Subcutaneous Tissue Density/Fibrosis

Subcutaneous tissue density and fibrosis are being assessed using one method, namely tonometry. Tonometry will be assessed at two or 3 time points depending on study group, at baseline (prior to first treatment), and after the final treatment on day 5 and day 12 if applicable. A repeated measures mixed linear model will be used to determine the changes in subcutaneous density at these time points. Randomised group will be forced into the model. Other covariates considered for inclusion in the model will include BMI, time of day measurements are taken, activity level (number of hours upright and ambulatory), age and number of hours utilizing compression garments.

8.2.3. Analysis of Patient Reported Outcomes.

Patients' self-reported symptoms and change in symptoms are recorded using the MYMOP questionnaire. Analysis will be undertaken to compare the intensity of the self-reported symptoms using a repeated measures analysis, with BMI, activity level (number of hours upright and ambulatory), age and number of hours utilizing compression garments.

8.3 Adherence to Therapy

Adherence will be evaluated by investigating the number and reasons for withdrawal for patients who fail to complete the pre-specified number of treatments and visits along with compression garment compliance and at home device usage for Group A.

9.0 Safety and Adverse Events

9.1 Risk Analysis: The subjects enrolled in the study are not expected to be at any higher or additional risk than those who use non-study pneumatic compression devices. There is risk with using any pneumatic compression device. These may include, but are not limited to risk of explosion if the device is used in the presence of flammable gases, risk of electrical shock if

the device is immersed in water or if the housing is broken and subject attempts to service the unit.

Pneumatic compression devices are contraindicated for use in the presence of pulmonary edema, thrombophlebitis, congestive heart failure, deep vein thrombosis, episodes of pulmonary embolisms, acute cancer, acute infection, and inflammation or other conditions where increased lymphatic return is undesirable. Clinical trials have not been completed to show the safety of using the FT garments during pregnancy and therefore should not be used.

There are minimal side effects expected from the treatment subjects will receive in this study. The expected risks are often a failure to respond to the treatment intervention and are not related to the treatment itself. In some cases, side effects due to lymphoedema can be serious, long lasting, or may be permanent. The risks listed below are symptoms of lymphoedema and may be experienced by all subjects with lymphoedema:

Likely:

- Pain or discomfort
- Increased swelling

Less Likely:

- Cellulitis – Infection of the skin which may include swelling, redness, and tenderness of the infected tissue
- Development of or increased edema in the truncal and/or genital region.

Ultrasound, bio-impedance and moister meter are procedures with minimal risk involved.

9.2 Adverse Events Reporting: All adverse events (related or not related to the device treatment) that occur throughout the conduct of the study will be reported. An adverse event is defined as any undesirable experience associated with the use of a medical product.

Anticipated Adverse Events

Adverse events associated with lymphoedema may include, but are not limited to: cellulitis, deep vein thrombosis, increased swelling.

All adverse events are to be reported to TSTI at the time of occurrence or when the Investigator becomes aware of the adverse event (e.g., at the follow-up evaluation).

TSTI may request that additional information such as operative notes, discharge summaries, lab reports, and a physician's summary of the event, be provided to TSTI as supporting documentation for any reported adverse event.

In the event of a subject death, a death summaries and autopsy reports will be provided to TSTI.

Serious Adverse Events

A serious adverse event is any adverse event that affects subject health or safety, that is life threatening, results in disability or permanent damage, or requires intervention to prevent permanent impairment/damage, or an event that results in hospitalization (initial or prolonged) or causes congenital or anomaly/birth defect, or results in death.

It is the responsibility of the Principal Investigator to notify their EC of any adverse events, as required. Serious adverse events will be reviewed by TSTI and the final determination as to whether or not an event is related to the device or treatment will be made by TSTI. If a serious adverse event is deemed related by TSTI, TSTI will report the event to the appropriate regulatory body and to all reviewing EC and participating investigators within 10 working days after TSTI first receives notice of the event, as required.

The protocol is specifically designed to minimize risks through careful subject selection (reference section 5.1.1 Inclusion Criteria and 5.1.2 Exclusion Criteria), rigorous adherence to a standardized schedule of treatment visits and routine clinical monitoring by TSTI representatives.

9.3 Subject Withdrawal: Subjects may voluntarily withdraw at any time, for any reason. Reasons for withdrawal will be recorded if the subject is willing to share this information. Subjects will be withdrawn from the study if they experience a serious adverse event or for any other reason set forth in section 5.1.3 or if in the investigator's judgment the subject develops an unrelated illness which will significantly affect assessment of the subject's clinical condition. The data from the withdrawn subjects will be included in the intent to treat analysis.

Withdrawn subjects will be replaced according to the following process:

- After all randomisation assignments have been assigned via the randomisation scheme. The site will review the subject withdrawal list and replace the subject according the sequence of subject withdrawal. For example: If first subject withdrawal is from Group A then the second from Group C. The next eligible subject would be enrolled in Group A followed by Group C. This will continue until there are 10 subjects completed in each study group for a total of 30 completed subjects.

10.0 Deviations from the Clinical Protocol: Any deviation from this Clinical Protocol undertaken to protect the life or physical well-being of a subject in an emergency

situation must be reported to the sponsor and the respective EC as soon as possible, but in no event later than five (5) working days after the emergency occurred. Anticipated deviations from this plan in a non-emergency situation must be pre-approved by the sponsor via telephone, e-mail, fax, or mail. It is preferred that deviations scheduled to be performed in a nonemergency situation not be conducted until written authorization via fax, mail, or e-mail is provided by the sponsor. All protocol deviations must be documented. Deviations that may affect the scientific soundness of the study, or the rights, safety or welfare of the subjects must also be reported to the reviewing EC according to their reporting requirements. Protocol deviations may necessitate the discontinuation of the subject from the study.

11.0 Subject Compensation: The sponsor agrees that it is responsible for the reasonable and necessary costs of diagnosis, care and treatment of any undesirable side effects, adverse reactions, illness or injury to a subject in the Investigation which are determined to result from participation in the Investigation, except for cost as a result of (i) any failure of Institution, Site Principal Investigator or any of the employees or agents of the Institution, Principal Investigator or Co-Investigator, to conduct the investigation in compliance with the clinical protocol, (ii) violation of any law, including the Health Insurance and Portability Act (HIPAA) (iii) any negligent or willful acts or omissions of Institution, Site Principal Investigator or Co-Investigator (iv) any misuse of the device by the Institution, or Site Principal Investigator or any Co-Investigator or any of the employees or agents of the Institution, Site Principal Investigator or Co-Investigator or (v) medical problems caused by failure of the subject to follow study instructions. Subjects may be provided reasonable reimbursement for time and/or parking/travel costs arising out of their participation in the trial. Subjects will not be otherwise compensated for their participation in the study.

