Pneumatic compression devices (PCDs) have been utilized for many years as an adjunct to home lymphoedema care. PCD treatment is intended to assist with limb volume control for patients with lymphoedema. In many cases, the aim is to simulate and potentially replace the conventional self-manual lymphatic drainage (MLD) component during Phase II of Complete Decongestive Therapy (CDT) in patients suffering from lymphoedema. The Flexitouch® system (FT) is an advanced PCD that was developed to aid in lymphoedema management at home.

Though there have been a number of publications on the use of PCD for the treatment of lower extremity lymphoedema, none have had the aim to define the optimal treatment dose with regards to pumping pressure, frequency of treatment session, and duration of the treatment session.¹⁰ Treatment duration in the literature can range from intensive treatment of 6 to 8 hours per treatment session to a less time intensive treatment regimen of as little as 30 minutes to 1 hour per session.^{15,16} Additional studies are needed to further address the optimal dose including duration and pressure.¹⁶ Tactile Systems Technology, Inc (TSTI) the makers of the Flexitouch ® system (FT) is dedicated to improving the lives of patients with lymphoedema and chronic swelling conditions through ongoing clinical research to determine optimal treatment.

Compression garments are often part of standard care for patients with lymphoedema. For the purposes of this study that is designed to evaluate the physiologic impact of pneumatic compression device dosing, the compression garment usage will not be formally evaluated. However the compression garments will be standardized across all study patients, mandating knee high compression garments with a pressure of 30–40 mmHg. If it is determined by data collection or clinical assessment that the garments variable is influencing the FT effect then the type and use of garment will be further controlled in future studies.

[figure not shown]
3.2 Device Description and Intended Use:

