12.0 General Study Information

12.1 Technical Support: Training and support for study procedures will be provided by the Sponsor contact listed in Section 1.1 or designee.

12.2 Discontinuation of the Study: The study may be terminated if:

- That the rate of severe adverse events in any arm of the study is such that the Ethics Committee decides continued participation would compromise subject safety. If deemed necessary by the Ethics Committee, a follow-up safety analysis will be performed for all subjects.
- Target subject accrual has not met, and cannot meet subsequent trial objectives.

Upon study termination by Sponsor, Sponsor will compensate Institutions for actual Study costs incurred through the close out of the Study, in accordance with the terms of the study contract.

12.3 Record Retention: Records must be maintained for a period of at least ten years after the date on which the study is completed or terminated. Investigator or Institution shall notify Sponsor at least thirty (30) days prior to any planned archiving or destruction of records related to this study. The recordings from the patient interviews will be transcribed and the recording then deleted. The transcription will be maintained with the study records.

12.4 Quality Assurance Procedures: This study will be conducted in accordance with Good Clinical Practice and International Conference on Harmonization Guidelines, NHS Trusts, institutional research policies and procedures and other appropriate regulatory requirements to ensure subject safety and quality of clinical procedures related to the conduct of the clinical trial. The investigators will permit regular monitoring, audits and site inspections by the EC, the sponsor, government regulatory bodies and any institution compliance and quality assurance groups of all study related documents (e.g. source documents, regulatory documents, data collection instruments, study data, etc.). The investigator will ensure the capability for inspection of applicable study related facilities. Regular trial monitoring will be conducted to ensure compliance to this protocol.

12.5 Materials Provided by the Sponsor: Sponsor will provide administrative study materials along with the FT controllers and garments, PicoPress® and pedometers.

12.6 Materials Provided by the Site: Institution will provide assessment equipment (scales, lab tests, perometer, bio impedance equipment, tonometer, clinical and support staff) needed to complete the trial.

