- All correspondences relating to the conduct of this study between the site and sponsor, ECs, and study monitor
- Curriculum Vitae and professional license for all study personnel, if applicable
- Site personnel signature and documentation regarding the Investigator's delegation of responsibility
- Clinical Site Visit log
- Protocol/device related training records for all applicable study personnel
- Investigational device inventory information including the date, quantity and serial number of all devices and received identification of all subjects who received treatment, and final disposition of the devices.
- Screening log
- Financial Disclosure documentation for the Investigator and Co-Investigators, if applicable
- Reports (see Table 1)

The following records must be maintained for each subject enrolled:

- Signed and dated informed consent forms
- Completed CRFs, queries and source document worksheets (if applicable)
- Complete medical records including procedure reports, lab reports (if applicable), etc.
- Records pertaining to a subject's death during the investigation

Investigators are required to prepare and submit to the sponsor or its designees complete accurate and timely reports on this investigation as required by regulations. The types of reports to be submitted are summarized in Table 1.

Table 1: Investigator Reports

Reports	Submit To	Timeframe
Unanticipated Adverse Device Event	Sponsor and Reviewing EC	As soon as possible but no later than 10 working days
Withdrawal of EC Approval	Sponsor	Within 5 working days
Progress	Sponsor, Monitor and Reviewing EC	Annually, at a minimum
Final	Sponsor and Reviewing EC	Within 3 months following the completion or termination of the Investigator's part

Subject study records, correspondence files, all supporting study documentation, and reports must remain on file at the investigational site for a minimum of ten years after the conclusion of this study or when it is no longer needed to support a marketing application, whichever is later. All investigators must contact Tactile Systems prior to destroying or archiving off-site any records and reports pertaining to this study to ensure that they no longer need to be retained on-site.

Additionally, Tactile Systems must be contacted if the Investigator plans to leave the investigational site to ensure that arrangements for a new Investigator or records transfer are made prior to the Investigator's departure.

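### Only the device maker's own finding that a serious adverse event is related triggers the sponsor's report to the regulator, all reviewing ethics committees and participating investigators (Section 9.2)

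*Combined protocol and SAP*

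**What the plan says.** All of this is in the combined protocol and SAP. Section 3.1 identifies TSTI as the maker of the Flexitouch system, and TSTI acts as sponsor throughout.

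Section 9.2 sets the scope of reporting widely: "All adverse events (related or not related to the device treatment) that occur throughout the conduct of the study will be reported". Sites send these events to TSTI when they occur or when the investigator learns of them.

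The paragraph of 9.2 on serious adverse events then lays down three rules:

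- The investigator's duty: "It is the responsibility of the Principal Investigator to notify their EC of any adverse events, as required".
- Who decides on causality: TSTI reviews each SAE, and "the final determination as to whether or not an event is related to the device or treatment will be made by TSTI".
- What follows from that decision: "If a serious adverse event is deemed related by TSTI, TSTI will report the event to the appropriate regulatory body", and also "to all reviewing EC and participating investigators within 10 working days after TSTI first receives notice of the event, as required".

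Section 13.4, Table 1, adds a separate duty. The investigator reports an unanticipated adverse device event to the sponsor and the reviewing EC, with the timeframe "As soon as possible but no later than 10 working days".

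Section 12.2 allows the study to be stopped if "the rate of severe adverse events in any arm of the study is such that the Ethics Committee decides continued participation would compromise subject safety".

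**The concern.** The company that makes the device has the last word on whether its device or the treatment caused a serious event. The only report for which 9.2 names the regulator and all participating investigators as recipients depends on that answer being yes. The text does not say that the investigator's view of causality is recorded or kept, or that it can trigger the report. It names no independent adjudicator or safety board.

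The rule matters most where causality is hard to judge, and 9.1 and 9.2 suggest that this will be common. They describe expected risks as often reflecting a failure to respond rather than the treatment itself, and they list cellulitis, deep vein thrombosis and increased swelling as events that go with lymphoedema. Section 9.1 also lists deep vein thrombosis and acute infection among the conditions in which pneumatic compression is contraindicated. For such an event, the clinician who examined the subject may reasonably differ from the sponsor. At stake is whether the regulator and other investigators hear of an SAE that the treating side thinks the device caused.

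**Working it through.** No arithmetic applies, because the rule depends on no error rate, effect size or sample size. The check is to take one case, an SAE that the investigator judges related and TSTI judges unrelated, and follow it along every reporting route in the text.

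| Route | Source | Does the text require a report in this case? |
|---|---|---|
| Site to TSTI | 9.2, all adverse events | Yes, whatever the causality |
| Investigator to own EC | 9.2, Principal Investigator's duty | Yes, subject to the words on what is required; does not depend on TSTI's finding |
| Investigator to sponsor and reviewing EC | 13.4, Table 1 | Only if the event is an unanticipated adverse device event |
| TSTI to regulator | 9.2, conditional sentence | No stated duty |
| TSTI to all reviewing ECs | 9.2, conditional sentence | No stated duty |
| TSTI to participating investigators | 9.2, conditional sentence | No stated duty |

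Three steps follow.

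1. The last three routes share one condition, TSTI's positive finding. When it fails, all three close together.
2. The second and third routes do not replace them. Both end at the sponsor or an EC, and neither names the regulator or other investigators.
3. The third route is narrower than it looks. Table 1 concerns unanticipated events, and 9.2 lists cellulitis, deep vein thrombosis and increased swelling under anticipated ones. The documents do not define the Table 1 term. On its ordinary meaning, a serious cellulitis or thrombosis would fall outside it.

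So the event reaches TSTI and the investigator's own EC, and no stated duty takes it further.

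**The case against.** The best answer is that the plan reports more than the conditional sentence suggests. All adverse events go to TSTI regardless of causality. The investigator notifies their own EC whatever TSTI concludes. Table 1 gives a second route for unanticipated device events, and the EC's power to stop in 12.2 looks at severe events by arm with no relatedness filter. This stands. It would be wrong to infer that reporting as a whole depends on TSTI's finding; only the sponsor's onward report does.

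A second answer is that the qualifier on what is required, together with the Good Clinical Practice clause in 12.4, may bring in outside rules that already give the investigator's judgment effect. That cannot be settled from the documents. The qualifier attaches to the sponsor's duty as well as the investigator's, so it does not discount one more than the other. The clause in 12.4 is general and states no causality rule. What remains is that 9.2, followed as written, does not require the report.

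Three stronger readings are tempting but are not supported:

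- **Biased counts of related events by dose.** The safety endpoint in 5.3 concerns how often complications occur and how severe they are, and Section 8 plans no analysis by relatedness. All arms use the same device, program and pressure setting, so an interest in finding events unrelated would apply to each of them. The site also knows the arm, because the envelope is opened with the subject present.
- **Delay.** The 10 working days run from TSTI's first notice of the event, not from its causality decision. The text supports possible non-reporting, not late reporting.
- **A size of 10 percentage points per event (1/10).** The plan defines no rate of related SAEs. Under 9.3 a subject with an SAE is withdrawn and replaced but stays in the intent-to-treat analysis, so that arm would have at least 11 subjects and the figure would be at most 1/11, about 9.1 points.

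Nor do the documents describe a formal investigator rating that TSTI would change. The case report forms are not among them. All that can be said is that a final determination by TSTI prevails over any other view.

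**Conclusion.** The point holds as a gap in SAE reporting. TSTI, the device maker, decides relatedness, and its positive finding alone triggers the sponsor's report to the regulator, all reviewing ECs and participating investigators. An SAE that only the investigator judges related has no stated route to the regulator or to other investigators.

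The size cannot be given as a number. No planned endpoint, estimate or comparison changes, so this is an inexpensive improvement to safety reporting and not a threat to the trial's results.

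The conclusion assumes that 9.2 is followed as written and that no outside rule fills the gap. Its reach also depends on the number of sites, which the plan leaves open: 6.2.2 allows for more than one, while 9.3 speaks of a single site. With one site and one EC, the main recipient left out is the regulator. With several, other ECs and investigators are left out too.

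**What to change.** In Section 9.2:

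- Record the investigator's causality assessment for every SAE, alongside TSTI's.
- State that the sponsor's report to the regulator, all reviewing ECs and participating investigators is triggered if either the investigator or TSTI judges the event related, with the existing limit of 10 working days from first notice unchanged.
- State that TSTI may add its own assessment but may not override the investigator's for the purpose of reporting.

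The cost is a sentence or two of protocol text, one recorded assessment per SAE (a new case report form field if none exists) and possibly a few more reports. Sample size, schedule and analysis are unaffected.

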- Individual with pacemaker or other implanted electronic devices
- Inability or unwillingness to remove bandaging from treatment regimen while participating in the study.
- Pregnancy
- Any condition where increased venous and lymphatic return is undesirable
- Inability or unwillingness to participate in all aspects of study protocol and/or inability to provide informed consent
- Currently participating in another clinical trial
- Currently using diuretics
- BMI > 40

6.1.3 Exit/Discontinuation Criteria: Subjects may exit the study prior to completion of all study visits if they meet any of the following criteria. The data collected as part of the study will be included in the intent to treat analysis.

- Subject death
- Subject voluntarily withdraws
- Subject experiences a serious adverse event that in the investigator's clinical judgment necessitates study discontinuation
- Subject acquires any of the exclusion criteria during treatment phase of the study

** Clinical assessment of lipoedema and lipolymphoedema will be completed to assure that the subject meets enrollment criteria. Lipoedema is a type of lipodystrophy, which can cause enlargement of the legs and be confused with lymphoedema. It is a clinical diagnosis with no specific diagnostic tests available. The typical pattern of lipoedema is excess fat deposition in the lower part of the body from the hips to the ankles, commonly with a history of bruising and tenderness. Patients also exhibit asymmetrical weight loss on dieting with weight being lost in the upper part of the body rather than the legs. Pure lipoedema is non pitting.*

Lipolymphoedema is the term used when patients with lipoedema develop superadded oedema. This typically forms around the ankles and feet and is pitting in nature. The diagnosis of lipolymphoedema is made by applying the

diagnostic criteria for lipoedema but with the presence of pitting oedema in the ankles and feet.

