8.2 Efficacy Analysis

Analysis will be undertaken for the following groups:

Group A: One lower extremity treatment per day using program L1 with the pressure set to “normal” utilizing the full garment set over 12 days. Total number of treatment hours=12.

Group B: Two lower extremity treatments per day (am and pm) using program L1 with pressure set to “normal” utilizing the full garment set over 5 days. Total number of treatment hours=10.

Group C: Two consecutive treatments 2 times a day (am and pm) using program L1 with pressure set to “normal” utilizing the full garment set over 5 days. Total number of treatment hours=20.

This study is planned to have a maximum of 30 completed subjects, 10 in each group with unilateral or bilateral primary or secondary leg lymphoedema. Each subject will receive the FT as per the groups described above. This small sample size will not offer a powered statistical analysis for any single outcome measurement, but is designed to estimate treatment effects for each proposed endpoint for evaluation in a subsequent clinical trial. This study is designed to determine both which measurement endpoints are most sensitive to the variable dosing protocols and to determine which endpoint should be defined as the primary end-point in a larger investigation of compression “dosage”. The study will be used to find the effect size for comparisons between the doses and from this to estimate a suitable sample size for a definitive study.

Subjects with missing data for the study outcomes will be included in the intention to treat analysis. However, the study will continue to enroll until there are 10 subjects in each arm that complete all study visits. After 30 patients have been randomised, those patients who fail to complete all treatment visits will be replaced until all data are available for 10 subjects in each study group. Data from the subjects who fail to complete will be used to determine the adherence to therapy in each randomised group.

Study analysis will be conducted for “within day” change as well as “between day” change. “Within day” change is defined as a comparison of pre-treatment measures against post-treatment measures following the last treatment of the day. “Between day” change is defined as a comparison of pre-treatment outcomes on treatment day 1 compared to post-treatment outcome measures on the final treatment day (day 12 for group A, day 5 for groups B and C).

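### Sections 9.3, 6.1.3 and 5.3 disagree on withdrawal after a serious adverse event, and a subject who stops the device has no planned final-day measurement

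*Combined protocol and SAP*

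**What the plan says.** Three sections deal with leaving the study because of an adverse event.

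- Section 9.3 is mandatory: "Subjects will be withdrawn from the study if they experience a serious adverse event". It extends this to any other reason in a section 5.1.3. It then adds a separate ground that does depend on judgment: "if in the investigator's judgment the subject develops an unrelated illness which will significantly affect assessment of the subject's clinical condition".
- Section 6.1.3 is permissive: "Subjects may exit the study prior to completion of all study visits if they meet any of the following criteria". The relevant criterion is: "Subject experiences a serious adverse event that in the investigator's clinical judgment necessitates study discontinuation".
- Section 5.3 has a clinician assess signs such as infection, DVT, cellulitis and pain, and treats discontinuation as a possible need.

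The definition in 9.2 opens: "A serious adverse event is any adverse event that affects subject health or safety". It continues with life-threatening events, disability, hospitalisation, death and similar outcomes. Section 9.1 lists "Pain or discomfort" and increased swelling as likely.

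Sections 6.1.3, 8.2 and 9.3 all keep subjects who leave, or who have missing data, in an intention-to-treat analysis. Section 8.2 also states that "those patients who fail to complete all treatment visits will be replaced until all data are available for 10 subjects in each study group". It defines the between-day outcome as the change from before treatment on Day 1 to after treatment on the final day: Day 12 in Group A, Day 5 in Groups B and C.

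**The concern.** A rule that removes subjects from a dose-comparison trial decides who has an endpoint. If two sections give different rules, two investigators can treat the same event differently and both be following the protocol. If the event that triggers the rule is itself ambiguous, the uncertainty grows.

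Loss caused by poor tolerance is informative: the missing final-day value is related to how the subject was responding, and the loss may differ between regimens. The study exists to estimate effect sizes between regimens and to size a definitive trial from them. Missing final-day values therefore bear on its main product, even though no hypothesis test is powered.

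**Working it through.** The plan has no sample-size calculation or event rate to reproduce. Its only figure here, 3 arms × 10 completers = 30, is consistent. The check is mainly a comparison of the texts.

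**Step 1: the withdrawal rules.**

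| Section | Force | Who decides | Trigger |
|---|---|---|---|
| 9.3 | mandatory | nobody; automatic | any serious adverse event |
| 6.1.3 | permissive | investigator | a serious adverse event judged to require discontinuation |
| 5.3 | possible need | clinician | signs, symptoms or complications |

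The judgment wording in 9.3 belongs to the unrelated-illness clause and does not reach back to the serious-event clause. A subject with a serious adverse event that the investigator thinks compatible with continuing must leave under 9.3 and may stay under 6.1.3. The pointer to 5.1.3 does not settle the matter: the exit criteria are numbered 6.1.3. Section 9.2 has the same slip, citing 5.1.1 and 5.1.2 for the eligibility criteria in 6.1.1 and 6.1.2.

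**Step 2: the trigger.** The sentence in 9.2 has two readings.

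- *Broad:* an effect on health or safety is the first item in a list of alternatives and is enough by itself. Since 9.2 also defines an adverse event as any undesirable experience, some ordinary events would then be serious.
- *Narrow:* the serious outcomes that follow qualify the opening phrase. Ordinary pain or swelling would then not be serious.

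Under 9.3 the reading decides who must be withdrawn and so who is replaced.

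**Step 3: what data remain.** The schedule in 7.2 has columns for screening, Day 1, other treatment days, and Day 5 (all groups) with Day 12 (Group A). It has no visit for a subject who stops early, and no section keeps such a subject in follow-up. For a subject withdrawn before Day 5:

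- Bioimpedance, tissue water and perometry are taken before and after treatment at each visit, so values up to withdrawal can enter the 8.2.1 mixed models. The final-day value is missing.
- Tonometry is analysed in 8.2.2 only at baseline, Day 5 and, in Group A, Day 12. The subject contributes baseline only.
- MyMOP and tissue ultrasound are scheduled in 7.2 only on Day 1 and on Day 5 or Day 12. Again only baseline remains.

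**Step 4: size.** One withdrawal is 1/10 = 10% of an arm's planned completers. To show how the number could vary, assume a constant daily withdrawal risk *h*, equal in all arms. These rates are assumptions, not figures from the plan. The proportion lost is *d* = 1 − (1 − *h*)^*D*, with *D* = 12 days in Group A and 5 in Groups B and C. The expected number randomised per arm to obtain 10 completers is 10/(1 − *d*).

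| *h* (assumed) | Lost, Group A | Lost, B or C | Randomised, A | Randomised, B or C (each) |
|---|---|---|---|---|
| 0.5% | 5.8% | 2.5% | 10.6 | 10.3 |
| 1% | 11.4% | 4.9% | 11.3 | 10.5 |
| 2% | 21.5% | 9.6% | 12.7 | 11.1 |
| 5% | 46.0% | 22.6% | 18.5 | 12.9 |

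Duration alone would make loss unequal between arms. Daily treatment runs the other way: 12/12 = 1 hour in Group A, 10/5 = 2 in Group B and 20/5 = 4 in Group C. If risk rises with daily hours, the direction could change, so the documents do not show which arm would lose more.

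**The case against.** The strongest reply is that 9.3 is a drafting slip. It refers to any *other* reason in the misnumbered exit list, which suggests that its serious-event clause is shorthand for the criterion in 6.1.3; section 5.3 also leaves discontinuation to assessment. This is plausible and makes the repair easy. It does not remove the conflict, because site staff must act on what 9.3 says.

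Three stronger conclusions are tempting, and the documents do not support them.

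- *A reader might infer that the likely events in 9.1 force withdrawal, perhaps of several subjects per arm.* That needs the broad reading of 9.2. The broad reading makes the later criteria, death included, redundant. Section 9.2 also lists increased swelling under anticipated events, apart from serious ones, and 9.1 says that effects of lymphoedema can be serious only in some cases. With no event rate given, no such count can be supported.
- *A reader might infer that the mandatory rule fills the arms with subjects who tolerate treatment.* Continuing to 10 completers per arm comes from the replacement rule in 8.2, which applies to anyone who fails to complete the treatment visits. It would operate whichever withdrawal rule is chosen.
- *A reader might infer that inflated counts would undermine early termination under 12.2.* That section speaks of severe rather than serious events, sets no numerical threshold and leaves the decision to the Ethics Committee.

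It is also fair to say that withdrawn subjects are not discarded: earlier fluid measurements count, and 8.3 reports the number of and reasons for withdrawals. The study is openly an unpowered pilot. These points limit the harm, but they do not supply the missing final-day values.

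**Conclusion.** The point holds as an unresolved contradiction with a consequence for the data. Sections 9.3, 6.1.3 and 5.3 cannot all be followed when a serious adverse event occurs that the investigator does not consider a reason to stop. The definition in 9.2 is ambiguous; it is not shown to be over-broad. Because stopping treatment is not separated from leaving the study, a withdrawn subject has no final-day value, while an intention-to-treat analysis and a baseline-to-final-day outcome are both promised.

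The size per case is one tenth of an arm's planned completers. The number of cases is unknown and may be small over 5 to 12 days. The figures in the table rest wholly on assumed risks. The contradiction and the missing final-day value do not depend on them, or on which reading of 9.2 is right.

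**What to change.** 1. Reconcile 9.3, 6.1.3 and 5.3 so that one withdrawal rule applies. Which rule is for the clinical team.
2. Correct the pointer in 9.3 from 5.1.3 to 6.1.3, and the similar pointers in 9.2.
3. Clarify the serious adverse event sentence in 9.2 so that it has one reading.
4. State in 9.3 that a subject who stops device treatment is asked, if willing, to attend the Day 5 measurements (in Group A also those of Day 12) and is analysed in the assigned group. Show this in the 7.2 schedule.

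Items 1 to 3 cost only wording. Item 4 costs one or two measurement visits per affected subject, at time points already in the schedule. Some subjects will decline, so it reduces the missing final-day data but does not eliminate it.
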